OBJECTIVES: The objective of this study is to evaluate the safety and hemostatic effectiveness of EVARREST Fibrin Sealant Patch (EVARREST) in controlling mild or moderate soft tissue & parenchymal bleeding during open hepatic, abdominal, pelvic, retroperitoneal, and thoracic (non-cardiac) surgery in pediatric patients.

STUDY DESIGN: This is an open label, prospective, multicenter, single arm clinical study evaluating EVARREST as an adjunct to hemostasis when conventional methods (i.e. suture, ligature, cautery) of controlling mild or moderate bleeding are ineffective or impractical during surgery in pediatric patients.

For this study, approximately 12 sites in US and UK will be utilized for consecutive screening and enrollment.

At least thirty-five (35) pediatric subjects with an appropriate mild or moderate bleeding TBS will be enrolled in this study. The age of the subjects enrolled in the study will be from 1 month to <18 years. This will include a minimum of 4 subjects aged 1 month (≥ 28 days from birth) to <1 year.

All subjects will be followed post-operatively through hospital discharge and at 30 days (+/-14 days) post-surgery.

TBS DEFINITION: The **Target Bleeding Site (TBS)** will be defined as the first accessible mild or moderate bleeding site identified in the hepatic parenchyma or soft tissue, where conventional methods of controlling bleeding are ineffective or impractical and is amenable to manual compression. The TBS must be a site where occlusion of the injured tissue surface blood vessels is required to achieve hemostasis.

The TBS must be an area that can have firm pressure applied and maintained continuously until 4 minutes after TBS identification, and to which EVARREST can be applied with a margin of 0.5-1 inch (1-2 cm). (Refer to Investigator's Brochure).

EVARREST should not be used on large defects in arteries or veins where the injured vascular wall requires repair with maintenance of vessel patency and which would result in persistent exposure of the EVARREST to blood flow and pressure during healing and absorption of the product. EVARREST should not be used in place of sutures or other forms of mechanical ligation for the primary treatment of major arterial bleeding.

Mild Bleeding: a TBS with a small area of capillary, arteriole or venule oozing

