EVARREST Sealant Matrix/EVARREST Fibrin Sealant Patch (EVARREST) is a topical absorbable hemostat and will be evaluated in this study to measure its safety and effectiveness in controlling mild/moderate bleeding from hepatic parenchyma or soft tissue as required by the Pediatric Research Equity Act (PREA) as a deferred pediatric study and as a Post marketing Requirement to Biologics Licensing Agreement (BLA) BL125392.

The Product

EVARREST is a sterile bio-absorbable combination product consisting of two constituent parts— a flexible backing and a coating of two biological components (Human Fibrinogen and Human Thrombin). The product has been developed for the management and rapid control of bleeding, including active, challenging bleeding.

The primary mechanism of action of EVARREST follows the principles of normal physiological fibrin clot formation. Upon contact with a bleeding wound surface, the biological components (Human Fibrinogen and Human Thrombin) on the matrix hydrate and the subsequent fibrinogen-thrombin reaction initiates the last step of blood clot formation in a normal and well-understood biochemical reaction. Hemostasis occurs when fibrinogen is converted into fibrin monomers, which spontaneously polymerize to a fibrin clot, forming a sealing layer that adheres to the tissue surface and integrates into the matrix. The matrix component provides physical support and a large surface area for the biological components, imparts inherent mechanical integrity to the product and supports clot formation. Natural healing occurs as the

product is absorbed by the body, which is expected to occur within approximately 8 weeks, CCI

CCI

The patch component provides a large surface area for the biological components and imparts inherent mechanical integrity to the product. The flexibility of EVARREST accommodates the physiological movements of tissues and organs.

Safety concerns potentially linked to the fibrinogen and thrombin components when used in fibrin sealants include the risks of viral transmission and anaphylactic and/or hypotensive reactions. CCI

EVARREST has been evaluated in the following clinical studies:

1. Phase I study to evaluate the safety of the product when used adjunctively in partial nephrectomy procedures. EVARREST was used in this study as an adjunct to hemostasis (after attempts to control bleeding with conventional surgical techniques had been made).

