7.1.4. Post-Surgery until Hospital Discharge

Prior to discharge, the following blood samples must be drawn and data will be recorded:

- Blood samples will be taken for Complete Blood Count (CBC) with Differential and Coagulation parameters (PT, aPTT and INR)
- Physical examination as per the institution's normal procedure
- Changes in concomitant medications
- Date of hospital discharge (for overall Length of Stay)
- Adverse events, including any complications potentially related to bleeding and/or thrombotic events

7.1.5. 30-day Follow-Up Visit (+/- 14 days)

The following information will be recorded either at the clinical follow-up visit approximately 30 days following surgery or via telephone if an in-person hospital visit is impractical:

- Changes in concomitant medications, including use of any blood products following hospital discharge.
- Adverse events, including any complications potentially related to bleeding and/or thrombotic events.

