9.7. Collection of Adverse Events

AEs will be recorded as they are reported, whether spontaneously volunteered or in response to questioning about well-being. AEs will be collected from the start of TBS identification, throughout the hospital admission, and until completion of the 30-day follow-up visit.

Details of all AEs occurring during the study must be recorded on the AE form with the following information:

- Description of the event
- Dates of onset and resolution
- Severity
- Action taken

- Outcome
- Relationship to investigational product
- Whether the AE is serious or not

All AEs will be documented in the subject's source documents (e.g. medical records) and eCRF. All AEs will be followed until completion of the 30-day follow-up visit or until a stable resolution, whichever is sooner.

Expectedness of an SAE will be defined based on whether the specificity or severity of which is not consistent with the current Investigator's Brochure.

Other: The investigator may also need to consider whether an event is attributable to the investigational product, based on insufficiencies or inadequacies in the instructions or as a result of user error.

The investigator must contact the Sponsor should this occur.

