- Laboratory tests (including hemoglobin, hematocrit, platelets)
- Estimated intra-operative blood loss

- Number and volume of blood products transfused

2 Treatment Assignment

This is a single-arm study in which all subjects will have EVARREST applied at the actively bleeding TBS during the surgical procedure.

3 Randomization and Blinding Procedures

As this is a single-arm study, no randomization will occur, and no blinding procedures are required.

4 Interval Windows

Interval windows for the purpose of analysis in this study will not be defined outside of those for visit scheduling. The final visit occurs approximately 30 days after surgery. There will be a window of 14 days around the scheduling of the 30-day follow-up visit, and any information entered in the eCRFs at this visit will correspond to the associated visit. There will be no assigning of observations to time points outside of the visit to which they are recorded in the eCRFs.

5 Primary and Secondary Endpoints and Associated Hypotheses

Study endpoints are presented under the Study Design section. No hypotheses testing will be performed for this study.

6 Levels of Significance

No formal hypothesis testing will be performed for this study. A two-sided 95% distribution-free confidence interval (CI) for median absolute time to hemostasis will be estimated. In addition, for success/failure secondary endpoints (4 and 10 minutes hemostasis endpoints), two-sided 95% CIs will be estimated for the proportion of successes in EVARREST treated subjects, using the Clopper-Pearson method. All CIs will be estimated for descriptive purposes only.

7 Analysis Sets

The following four analysis sets are defined:

- All Enrolled Set (AES) consists of all subjects who provided informed consent or assent form for this study.
- Full analysis set (FAS or intent-to-treat set) consists of all enrolled and eligible subjects for whom TBS was identified. Subjects who do not complete the procedure after TBS identification will be included in the FAS analysis.
- Evaluable analysis set (or per-protocol [PP] set) consists of all FAS subjects who have no major protocol deviations affecting the primary endpoint and have data available for this endpoint.
- Safety analysis set will consist of all subjects who received treatment.

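### The ±14-day window and the AE stop rule let safety collection and follow-up of open events, including SAEs, end as early as day 16, so 30 days of observation is not guaranteed

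*Protocol*

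**What the plan says.** The Protocol synopsis sets the schedule: "All subjects will be followed post-operatively through hospital discharge and at 30 days (+/-14 days) post-surgery". Section 7.1.5 repeats the window in its heading and describes the contact as "approximately 30 days following surgery or via telephone if an in-person hospital visit is impractical".

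Protocol 9.7 then makes that contact the end point of two processes.

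- Collection of new events: "AEs will be collected from the start of TBS identification, throughout the hospital admission, and until completion of the 30-day follow-up visit".
- Follow-up of events already recorded: "All AEs will be followed until completion of the 30-day follow-up visit or until a stable resolution, whichever is sooner".

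SAP 4 keeps the window ("There will be a window of 14 days around the scheduling of the 30-day follow-up visit") and rules out any re-windowing: "There will be no assigning of observations to time points outside of the visit to which they are recorded in the eCRFs". SAP 9.4.3 summarises AEs by number and percentage of subjects, in total and in three age groups. No summary of follow-up duration is described.

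On the product, Protocol 1 says the implant "product is absorbed by the body, which is expected to occur within approximately 8 weeks"; the text that follows is redacted.

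**The concern.** Safety is part of the study objective, and AEs potentially related to bleeding at the target bleeding site or to thrombosis are named endpoints. Both AE rules in Protocol 9.7 depend on when a site happens to make the last contact. Two consequences follow.

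1. **Unresolved events.** A thrombotic or bleeding SAE that is still open at a day-16 contact need not be followed further. Protocol 9.7 requires an outcome for every AE and SAP 9.4.3 tabulates it, but for such an event the recorded outcome may only be that it had not resolved. In a study of about 35 children, the eventual outcome of one or two serious events can carry much of the safety message.

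2. **Unequal observation.** Subjects observed for 16 days and for 44 days enter the same denominator with equal weight. Nothing in the planned output would show this. A difference in contact timing between the three age groups could not be separated from a difference in AE risk. The Protocol itself speaks of a 30-day follow-up period (4.3, exclusion criterion 7), so the percentages may well be taken as 30-day figures.

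**Working it through.** The plan gives no figure to reproduce here: there is no formal sample size calculation and no target AE rate. The check is calendar arithmetic, a reading of the stop rule, and one illustration on assumed rates. Surgery is taken as day 0.

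**Inputs.** Nominal contact day 30, window 14 days either side (Protocol synopsis and 7.1.5; SAP 4). Planned subjects 35 (Protocol 8.1). Absorption limit about 8 weeks (Protocol 1).

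**Step 1: range of compliant follow-up.**
- Earliest: 30 − 14 = day 16. Latest: 30 + 14 = day 44.
- Ratio: 44/16 = 2.75.
- Share of the 30 days missed with a day-16 contact: (30 − 16)/30 = 47%.
- For 35 subjects, 35 × 16 = 560 person-days if every contact were on day 16, and 35 × 30 = 1,050 if every contact were on day 30.

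**Step 2: how much of the window is early.** Days 16 to 44 are 29 permitted days. Days 16 to 29 are 14 of them: 14/29 = 48%.

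**Step 3: an even spread (assumption).** If contacts were equally likely on each of the 29 days:
- Mean shortfall before day 30: (1 + 2 + … + 14)/29 = 105/29 = 3.6 days, so the first 30 days are observed for 26.4 days on average.
- Mean excess after day 30: also 105/29 = 3.6 days, so mean total follow-up is 30 days.

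**Step 4: effect on seeing an event (illustration).** Assume a 30-day risk r for some event type and a constant daily hazard. Neither is in the documents. The risk by day d is 1 − (1 − r)^(d/30), and the chance that at least one of 35 subjects has the event observed is 1 − (1 − r)^(35d/30).

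| Assumed 30-day risk | All contacts day 16 | All day 30 | All day 44 |
|---|---|---|---|
| 3% | 43% | 66% | 79% |
| 5% | 62% | 83% | 93% |
| 10% | 86% | 98% | 99.6% |

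The day-16 and day-44 columns are extremes, not forecasts.

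**Step 5: the stop rule.** Under Protocol 9.7, an event open at the last contact reaches the contact before it reaches resolution, so the earlier-of-two rule ends its follow-up there. Protocol 9.8 sets reporting times only (24 hours for SAEs, two weeks for other AEs). Protocol 7.3 treats the 30-day visit as the point to which subjects should be kept in the study. The documents contain no later contact and no exception for serious or related events.

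**Step 6: absorption.** 8 × 7 = 56 days; 56 − 44 = 12. The latest compliant contact falls 12 days before the approximate limit.

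**The case against.** The strongest reply is that day 30 is the target and the window is symmetric. Subjects contacted on days 30 to 44 are observed for 30 days or more, and under an even spread mean follow-up is exactly 30 days (Step 3). Collection also runs through the hospital admission, so a long-stay child may be observed past day 16. The AE endpoint in SAP 1 covers the follow-up period, not a fixed 30 days, and no SAP table is labelled as 30-day incidence. The trial is single-arm and descriptive, so unequal follow-up distorts no treatment comparison. SAEs must be reported within 24 hours of awareness, and every AE record carries an outcome field.

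All of this stands, and it rules out three stronger readings.

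- A reader might infer that the trial fails to deliver 30-day safety. The documents show only that it does not guarantee it.
- A reader might infer that the window must bias incidence downwards. Early contacts lower the count relative to a fixed 30 days, late contacts can raise it, and the net direction is unknown.
- A reader might infer that stopping before 8 weeks is a design error. The Protocol gives an approximate upper limit, the continuation is redacted, and nowhere is follow-up said to span absorption. The Protocol's warnings about exposure during healing and absorption concern large vessel defects, which are excluded.

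The reply does not reach the stop rule for open SAEs, and it does not explain why actual follow-up time goes unreported.

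**Conclusion.** The point holds as a gap in the safety rules. AE collection and follow-up of open events, serious ones included, may end on day 16 in full compliance with the Protocol. Observation can run from 16 to 44 days, and the SAP neither adjusts for this nor displays it.

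The range, the 47% loss at day 16 and the 48% share of early days follow directly from the stated window. The 3.6-day mean shortfall needs an even spread of contacts, and the detection probabilities need an assumed risk and a constant hazard. The practical effect depends on when sites make contact, which the documents cannot show.

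This does not undermine the primary endpoint or invalidate the trial. It weakens a stated objective and should be corrected. The missing provision for open SAEs is the more important half. That follow-up ends before the approximate 8-week limit is at most a limitation to state in the report.

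**What to change.** 1. **Protocol 9.7.** Keep the present stop rule for other events, but follow SAEs and product-related AEs still open at the last contact until they resolve or stabilise.
2. **Protocol synopsis, schedule of events, 3 and 7.1.5; SAP 1 and 4.** Set the last contact at day 30 to day 44 (−0/+14), or at least require AE collection through day 30. Telephone contact stays available where a visit is impractical, as now.
3. **SAP 9.4.3.** Report actual follow-up days (for example median and range, overall and by age group) and the number of AEs and SAEs still open at last contact, beside the AE tables.

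Items 1 and 2 need a protocol amendment, which under Protocol 12.1 must be submitted and approved before use at about 12 sites. They also cost some scheduling flexibility and a few extra calls. Item 3 needs only a SAP change and dates the trial already records; it is worth making even if the window stays. No contact after 8 weeks is needed.

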9.8. Adverse Event Reporting

It is a requirement that the Investigator promptly reports all SAEs (irrespective of relationship to the study product) to PAREXEL, the safety monitoring CRO, as soon as possible, but no later than 24 hours after becoming aware of the event occurring. The SAE should also be entered into the electronic case report form (eCRF) on the CCI clinical trial database. SAE reports must be communicated as follows:

For US sites:

[contact]

Email: [contact]

PAREXEL International 1
[name]
[name] United
States
[contact]

For UK Sites:

[contact]

Email: [contact]

In the event that the site is unable to complete the SAE form to report the event within 24 hours of their knowledge of the event, the investigators may report the SAE over the telephone via the SAE answering service, and then provide the completed SAE form via fax or email.

[contact]

[contact]

Suspected, unexpected serious adverse drug reactions (SUSARs) will be reported to all relevant competent authorities, PIs, and IRBs /Ethics Committees within the required timeframes of seven calendar days for SUSARs that are fatal or life-threatening, and fifteen calendar days for all other SUSARs.

All other Adverse Events (AEs) must be reported (entered) into the CCI clinical trial database (electronic case report form (eCRF) within two weeks from the date the site becomes aware of the AE).

10. REGULATORY OBLIGATIONS

10.1. Informed Consent

Prior to participation, the study procedures and any known or likely risks will be explained to the subjects and/or their parent/legal guardian by the investigator or other medically qualified co-investigator. An Informed Consent Form will also be provided containing all the required information. Any questions will be answered and the patient and/or their parent/legal guardian will then be given sufficient time to consider their participation in the study before signing a consent form. Subjects and/or their parent/legal guardian should receive a copy of the Informed Consent Form. In addition, assent must be obtained from pediatric subjects who possess the intellectual and emotional ability to comprehend the concepts involved in the trial. If the pediatric subject is not able to provide assent (due to age, maturity and/or inability to intellectually and/or emotionally comprehend the trial), the parent/legal guardian's written Informed Consent for the subject will be acceptable for the subject to be included in the study.

The Investigator (or designee) will explain that the subjects and their parent/legal guardian are completely free to refuse to enter the study or to withdraw from it at any time, without any consequences for their further care and without the need to justify.

Each subject and/or their parent/legal guardian will be informed that the subject's source medical records may be checked by representatives from the Sponsor or from a regulatory agency, in accordance with applicable regulations. However, they should be made aware that all information will be treated with confidentiality, and a study ID code or number will identify them.

10.2. Institution Approval / Ethics Committees

The investigator must submit the Protocol and the Consent/Assent Form to the appropriate Institution department/EC according to local requirements. Approval from the Institution/EC must be obtained prior to starting any study-related procedure.

10.3. Data Management

10.3.1. Data Collection

The Investigator must maintain required records on all study subjects. Data for this study will be recorded in the subject's medical records, study-specific worksheets and on electronic CRFs provided by Sponsor in accordance with the parameters set forth in ICH GCP Guidelines - Responsibilities of Sponsor, Monitor and Investigator. All data on the eCRFs should be recorded with appropriate source documentation.

Each EDC eCRF will be completed by the PI or PI's designee. Every effort should be made to respond to all monitoring and/or data management questions on each eCRF as completion of the data is required by the protocol. A unique ID number will identify each subject. The unique ID number will be visible on each eCRF. At no time should the subject name appear on the eCRFs. Complete data is needed in order to provide statistical analysis for each subject. All data should be recorded accurately and completely. The Investigator is responsible for reviewing and approving each completed eCRF. Assurance of overall review and approval will be documented by the Investigator electronically signing each subject's electronic casebook.

10.3.2. Data Correction

Required data corrections to eCRFs will be prompted via automated electronic edit checks and/or queries manually created by sponsor reviewers. The change(s), individual making the change(s), and time the change(s) were made to the eCRFs will be automatically captured in the audit trail within CCI [REDACTED].

Investigators must keep accurate separate records (other than the CRFs) of all subjects' visits, being sure to include all pertinent study related information. A statement should be made indicating that the subjects have been enrolled in Protocol and have provided written Informed Consent. Any and all side effects and adverse events must be thoroughly documented. Results of any diagnostic tests conducted during the study should also be included in the source documentation. Telephone conversations with the subjects concerning the study must also be documented.

The Investigator is responsible for maintaining a Subject Identification Log, which will include all subjects who provided Informed Consent (i.e. to include treated subjects and screening failures). This confidential subject identification code provides the link between named subject source records in the subject file and anonymous CRF data provided to ETHICON.

The Investigator must retain all study related documentation until at least two years after the final marketing application is approved, or at least two years have elapsed since the formal discontinuation of the clinical study. Study documents should not be destroyed without prior written agreement between the Investigator and ETHICON. The sponsor must be notified if the Investigator wishes to assign the study records to another party or move them to another location.

